3. OBJECTIVES

Primary

- Reduction of time-to-response, defined by the achievement of laboratory blood marker response, confirmed at 48 hours after the initial reporting of this response

Secondary (including longer-term disease sequelae)

- Improvement in number of subjects responding to therapy
- Reduction in PE procedure-related items
- Reduction of time to resolution or improvement of symptoms typical of TTP, including blood markers
- Reduction of number of exacerbations (defined as recurrent thrombocytopenia following a response and requiring a re-initiation of daily PE treatment after ≥ 1 day but ≤ 30 days after the last daily PE) and relapses (defined as *de novo* event of TTP that occurs later than 30 days after the last daily PE)
- Improvement of cognitive level at steady state post acute phase
- Improvement of clinical symptoms and organ function
- Reduction in mortality within the PE treatment period and within the subsequent study drug treatment period (including tapering)
- Reduction of concomitant treatment-related complications
- Evaluation of safety and immunogenicity of adjunctive treatment with ALX-0081
- Determination of PK and PD characteristics of ALX-0081 in patients with acquired TTP

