 - 4 samples: prior to study drug and at 1-6 h, 6-12 h, 18-24 h post-study drug, but prior to next administration of study drug or before next PE (in case of tapering)
 - Subsequent time interval until the last day of study drug administration:
 - 2 samples once-weekly: prior to study drug administration (but after PE, in case of tapering) and 4-8 h post-study drug. Of note, for each day that a follow-up at the investigational site is planned, the

administration of 10 mg study drug will be performed during the follow-up visit in the investigational site.

- Blood samples for ADA (central lab) need to be taken on day 14, and then weekly until the last day of study drug administration.
- Blood sampling for ADAMTS13 and anti-ADAMTS13 antibody titre (central laboratory). This blood sampling needs to be performed on the first day after the daily PE period and 1 week post last day of PE (including tapering) and at 3 weeks post last day of PE (including tapering); the 1 week and 3 weeks after the very last PE (including tapering) sampling may be done at the weekly visit, even if not exactly 1 or 3 weeks.
- Retrieval of 30 mL from the first bag of pathological spent plasma resulting from the first PE procedure on study. This will be divided in aliquots of 5 mL each for storage at -70°C. The retrieved spent plasma, obtained from the first plasma exchange on study, and the first spent bag will be used for following purposes.
 - As matrix for development and validation of ADA, biomarker assays that will be used in TITAN trial.
 - For further characterisation of possible immunogenicity findings.
 - For additional measurement of vWF and ALX-0081 concentrations under R&D conditions and subsequent PK/PD modelling to assess extent of removal of these components upon plasma exchange.
- Recuperate nurse sheet and/or AE diary at each post discharge visit.

An overview of assessments performed during the treatment phase of this trial is provided in Table 11.

Assessments scheduled in case of TTP exacerbation

In case of TTP exacerbation, defined as recurrent thrombocytopenia following a response and requiring a re-initiation of daily PE treatment after ≥ 1 day but ≤ 30 days after the last daily PE, the assessments scheduled for “Day 1 after last daily PE” are not performed after completion of the exacerbation treatment, instead, the “post-daily PE (including tapering)” assessments are continued. A dedicated schedule of assessments is provided in Table 12.

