8.2 Assessment of Efficacy

8.2.1 Clinical Outcome

- Time-to-response of treatment, defined by a recovery of platelets $\geq 150,000/\mu\text{L}$. This response must be confirmed at 48 hours after the initial reporting of platelet recovery above $150,000/\mu\text{L}$ by a *de novo* measure of platelets $\geq 150,000/\mu\text{L}$ and LDH $\leq 2 \times \text{ULN}$
- Number of subjects with complete remission
- Number of (subjects with) exacerbations of TTP and time to first exacerbation of TTP. Exacerbation is defined as recurrent thrombocytopenia following a response and requiring a re-initiation of daily PE treatment after ≥ 1 day but ≤ 30 days after the last daily PE.¹
- Number of subjects relapsing of TTP (defined as *de novo* event of TTP that occurs later than 30 days after the last daily PE) for a maximum of 1 year, and time to first relapse of TTP
- Daily PE data, including serious adverse events (SAEs) related to daily PE treatment
- Neurocognitive function, as measured by a neurocognitive test battery, at complete remission and at 1 year follow up. This test will be preceded by the Glasgow Coma Score to measure the state of consciousness of the subject
- Improvement of organ dysfunction and improvement of TTP related signs and symptoms
- Total mortality within the daily PE treatment period and within the subsequent study drug treatment period (including tapering)
- Determination of biomarkers of TTP including but not limited to disintegrin-like and metalloprotease with thrombospondin repeats 13 (ADAMTS13) levels and anti-ADAMTS13 antibody titres (see also PD assessments)

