Complete remission: Complete remission is defined as recovery of platelets (confirmed by platelets  $\geq 150,000/\mu\text{L}$  and LDH  $\leq 2 \times \text{ULN}$  at 48 hrs after initial platelet response) and absence of exacerbation.

Initial platelet recovery: Date of initial platelet recovery is defined as the first occurrence of platelets  $\geq 150,000/\mu\text{L}$  which is **confirmed** 48 hours later by platelets  $\geq 150,000/\mu\text{L}$  and LDH  $\leq 2 \times \text{ULN}$ . For example, if platelets reach  $\geq 150,000/\mu\text{L}$  on Day 5, are not confirmed at Day 7, reach  $\geq 150,000/\mu\text{L}$  again on Day 10 and are confirmed at Day 12, the initial platelet recovery occurs on Day 10. Initial platelet recovery and confirmation dates will be determined using the actual lab results, following standardisation to consistent units.

Time to Response: Time to response will be calculated as the number of days, hours and minutes (represented by number of days with two significant digits after the decimal point) from study drug administration to initial platelet recovery, as defined above. An

---

observation is censored if the observation does not meet the defined time interval of 30 days, due to any cause of loss-to follow-up (including death), or endpoint not being reached.

Subjects that attain confirmed platelet response:

Time-to-Response = [Date and time (hrs, min) of initial platelet recovery] – [Date and time (hrs, min) of first study drug administration]

Exacerbation: Exacerbation of TTP is defined as recurrent thrombocytopenia following a confirmed platelet response and requiring a re-initiation of daily PE treatment  $\geq 1$  day but  $\leq 30$  days after the last daily PE.

Relapse: Defined as de novo event of TTP that occurs later than 30 days after the last daily PE.

First PE: Defined as start of PE.

First on-study PE: Defined as first PE received after randomisation.

In case first on-study PE is not first PE, then first on-study PE should be started within 24 hours (after the end) of the first PE. If not it is considered major protocol deviation.

Overall duration of study treatment exposure (days): Defined as date of last dose of study treatment – date of first dose of study treatment + 1

Duration of study treatment exposure during daily PE (days): Defined as date of last dose of study treatment during the daily PE period – date of first dose of study treatment during the daily PE period + 1

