**Table 1: Censoring/event scenarios (for ITT and PP analysis of confirmed platelet response)**

Case	Description	Time at risk/ Time to recovery of platelets (days)	Responder	Censored (No = 0; Yes = 1)
1	No event in 30 days of continuous daily PE a	30	No	1
2	At day 30, confirmed recovery of platelets (per protocol)	30	Yes	0

Case	Description	Time at risk/ Time to recovery of platelets (days)	Responder	Censored (No = 0; Yes = 1)
3	At day x b (1 st measurement of platelet recovery), confirmed recovery of platelets, ideal case (per protocol)	x	Yes	0
4	No event occurred and subject is no longer in trial at day x b (including replaced subjects who are dosed)	x	No	1
5	At day x b (1 st measurement of platelet recovery), subject has recovery of platelets, however, missing data at 48 hours later, and no subsequent confirmation on platelet count during daily PE (no more daily platelet measurements) c	x	No	1
6	No recovery of platelets, however, daily PE stopped (daily PE considered surrogate for response d ). Except if PE stopped due to AE e (then idem case 4)	Time of last daily PE	No	1
7	Subject not dosed (after randomisation)	1	No	1

a PE = plasma exchange.

b At day x within 30 days assessment period.

c No subsequent confirmation during daily PE, since daily PE has been stopped by Investigator for clinical response which does not meet protocol definition of response.

d Certain subject's platelet counts 'hover' around 150,000/ $\mu$ L, and in clinical practice, PE is stopped.

e Start and stop dates of adverse events related to PE will need to be compared to PE stop dates in order to identify PE stopped due to AE.

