### 6.3.2 Secondary Efficacy Variables

#### *Secondary Endpoints*

All endpoints achieved within 30 day period after end of study drug treatment:

- Number and percentage of subjects with complete remission (defined as confirmed platelet response and absence of exacerbation)
- Number and percentage of (subjects with) exacerbations of TTP (defined as recurrent thrombocytopenia following a confirmed platelet response and requiring a re-initiation of daily PE treatment after  $\geq 1$  day but  $\leq 30$  days after the last daily PE) and time to first exacerbation of TTP
- Number of daily PE sessions, number of total volume of plasma administered and number of days of daily PE
- Total mortality within the PE treatment period and within the subsequent study drug treatment period (including tapering)
- Number and percentage of subjects relapsing of TTP (defined as *de novo* event of TTP that occurs later than 30 days after the last daily PE)
- Number and percentage of subjects with platelets  $\geq 150,000/\mu$ L at day 30 of study drug administration (last treatment day visit) and one month follow-up time point
- Resolution or improvement (improvement of  $\geq 1$  grade in the CTCAE v4.0 scale) of TTP-related signs and symptoms as captured on physical examination and as adverse events, at complete remission and at end of the study drug treatment period (including tapering) (by number of unique subjects and by total number of AEs)
- Incidence of PE treatment-related AEs, such as, but not restricted to: haemorrhage from catheter insertion, sepsis, catheter thrombosis, pneumothorax, fluid overload, hypoxia, hypotension, anaphylactoid reactions and TRALI

---

This study has been statistically powered for the primary endpoint. No adjustment for multiplicity has been applied to the exploratory analysis for the secondary variables. All analysis will be performed on the ITT and PP populations and any p-values presented for secondary efficacy variables are purely exploratory (e.g. comparison of the number and percent of subjects with complete remission, exacerbations, relapse and daily PEs).

The number and percentage of subjects with complete remission at one month post first administration of study treatment, along with the exact binomial CI of the percentage will be presented by treatment group, overall and by ADAMTS13 activity  $< 5\%$  vs.  $\geq 5\%$  at baseline.

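### Exacerbation counts only after a 48-hour confirmed response, so early recurrences in subjects whose daily plasma exchange stopped unconfirmed fall into no outcome category

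*SAP*

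**What the plan says.** Exacerbation is worded in two ways, both with a window of 1 to 30 days after the last daily PE.

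- **After a confirmed response.** SAP 6.3.2: "recurrent thrombocytopenia following a confirmed platelet response and requiring a re-initiation of daily PE treatment". SAP Section 3: "Exacerbation of TTP is defined as recurrent thrombocytopenia following a confirmed platelet response and requiring a re-initiation of daily PE treatment". The secondary endpoint lists in the protocol synopsis and protocol 4.1.2 agree. SAP 6.3.1 explains confirmation: 48 hours after platelets first reach 150,000/µL, a new count is still at or above that level and LDH is at most 2 × ULN.
- **After a response.** Protocol Section 3: "recurrent thrombocytopenia following a response and requiring a re-initiation of daily PE treatment". The synopsis objectives, SAP 1.1 and the assessment schedule in protocol 8.1.2 say the same, as does protocol 8.2.1: "Exacerbation is defined as recurrent thrombocytopenia following a response and requiring a re-initiation of daily PE treatment".

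Protocol 7.2, on study drug, identifies an exacerbation by the time window alone.

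SAP Section 3 gives relapse as: "Defined as de novo event of TTP that occurs later than 30 days after the last daily PE". It sets no condition on an earlier confirmed response.

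SAP Table 1 foresees daily PE ending without confirmation. In case 5 platelets recover but the 48-hour data are missing; footnote c explains that "daily PE has been stopped by Investigator for clinical response which does not meet protocol definition of response". In case 6 daily PE stops with no platelet recovery, and footnote d refers to counts that stay close to the threshold. Both are coded as censored non-responders. SAP 6.1.5, which lists changes from the protocol, does not mention exacerbation.

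**The concern.** One stated objective is to reduce exacerbations. Take a subject whose daily PE is stopped on clinical grounds before confirmation, and who needs daily PE again a week later. A site using protocol 8.1.2 could reasonably schedule this as an exacerbation. The analysis definition cannot count it, because no response was confirmed. The relapse definition cannot either, because the event came too soon. SAP 6.3.2 also reports exacerbation and relapse combined, and the event is missing there too.

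So whether a subject can contribute an exacerbation depends on when daily PE was stopped and whether a 48-hour platelet and LDH sample exists. Investigators know the allocation (protocol 7.5), and stopping PE follows local guidelines and clinical judgement (protocol 4.3 and 7.1). The omitted share could therefore differ between arms. What is at stake is how completely the recurrence results describe early recurrence, and in some cases who is called a complete remission.

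**Working it through.** **1. The plan's own figure.** The documents give no rate or sample size for exacerbation. The only design figure is N = 110 for the primary endpoint (protocol 10.4, SAP 6.1.4). With HR = 6/3.36 = 1.786, one-sided 2.5% and 80% power, Schoenfeld's formula gives (1.960 + 0.842)² / (0.25 × (ln 1.786)²) = 7.849/0.0840 = 93.4, so 94 events. Then 94/0.85 = 110.6, so 111; allowing also for the 30-day event probability of 0.983 gives 113. The figure of 110 is reproduced closely and does not depend on the present point.

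**2. Every combination set against the definitions.**

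| State when daily PE stopped | Restart, days after last daily PE | Exacerbation (SAP 3, 6.3.2) | Exacerbation if any response suffices | Relapse |
|---|---|---|---|---|
| Confirmed response | 1–30 | yes | yes | no |
| Case 5: recovered, unconfirmed | 1–30 | **no** | yes | **no** |
| Case 6: no recovery | 1–30 | **no** | no, on plain wording | **no** |
| Any of these | over 30 | no | no | yes, if a new TTP event |

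The looser wording closes the gap for case 5 only. The gap is asymmetric: after an unconfirmed stop, a recurrence on day 31 can be a relapse and one on day 7 is nothing.

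**3. Could confirmation be missed under the schedule?** Protocol 8.1.2 and Table 11 schedule haematology and chemistry daily before PE, on day 1 after the last daily PE, then weekly. If platelets first reach the threshold on day *d* and day *d* is also the last daily PE, samples fall on *d* + 1 and then weekly. The confirming sample at *d* + 2 is not scheduled. A fall in platelets within those 48 hours also prevents confirmation.

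**4. Complete remission.** SAP Section 3 requires a confirmed response and no exacerbation, and its worked example shows that a later confirmation counts after an earlier failed one. Suppose daily PE stops unconfirmed, platelets fall, daily PE restarts, and the next recovery is confirmed. On that wording the subject has a confirmed response and no counted exacerbation, hence complete remission. A subject who never confirms cannot be a complete remission. Table 1 does not say how a case 6 subject who restarts daily PE is handled.

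**5. Size, by assumption only.** Let *u* be the share stopping daily PE unconfirmed, *r*₁ the early recurrence risk after confirmation and *r*₂ the risk without it. None is in the documents. Assume *u* = 5% to 20%, *r*₁ = 20%, and *r*₂ = 20% or 40%.

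- Uncounted events = 110 × *u* × *r*₂: low 110 × 0.05 × 0.20 = 1.1; high 110 × 0.20 × 0.40 = 8.8.
- Share of early recurrences uncounted = *u r*₂ / (*u r*₂ + (1 − *u*) *r*₁): low 0.01/(0.01 + 0.19) = 5%; high 0.08/(0.08 + 0.16) = 33%.
- If *u* differs by arm (5% against 20%), true recurrence is equal in the two arms, and recurrence does not depend on confirmation, the counted risk ratio is 0.80/0.95 = 0.84 or 0.95/0.80 = 1.19 instead of 1.00, depending on which arm has the larger share.

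**The case against.** The SAP has not drifted from the protocol: it repeats the secondary endpoint of protocol 4.1.2. The primary objective describes response as confirmed at 48 hours, so *a response* in the next list may simply be shorthand. Requiring confirmation also has a purpose. It separates a new fall from continuation of the same episode, and it ties the event to laboratory values when the decision to restart PE is itself unblinded. The subjects are not invisible, since their PE days and plasma volume are summarised. SAP 6.3.5 and 6.3.6 are redacted and might hold further recurrence analyses.

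Most of this stands, and it limits what can be claimed:

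- A reader might infer that the SAP contradicts the protocol endpoint. It does not; the tension is between objectives and endpoint inside each document, and it may be one of wording only.
- A reader might infer that adopting the objectives' wording would solve the problem. It would not cover case 6, where there was no recovery to follow.
- A reader might infer that the arm comparison is biased. The documents show a route by which omission could differ by arm, not that it does.

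None of this gives the events a category. If *response* means confirmed response throughout, the wording conflict goes and the unclassified recurrences remain. SAP Table 2 recodes cases 5 and 6 as platelet responders but leaves the exacerbation definition alone.

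**Conclusion.** The gap is real and follows from the text alone. A restart of daily PE for a renewed platelet fall, 1 to 30 days after the last daily PE, in a subject without a confirmed response, is absent from the exacerbation count, from time to first exacerbation and from the combined count. On SAP Section 3's wording it also does not prevent complete remission if a later recovery is confirmed.

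The size is unknown. The range of about 1 to 9 events, or 5% to 33% of early recurrences, rests wholly on assumed inputs, and its upper end needs both the largest unconfirmed share and a doubled risk. The documents do not establish that these subjects are at higher risk.

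A reader might infer that the trial's main conclusion is affected. It is not: the primary test and sample size do not use exacerbation, and SAP 6.3.2 calls secondary p-values purely exploratory. The point is still worth settling before database lock, because it changes what the recurrence results show.

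**What to change.** - Keep the confirmed-response exacerbation of protocol 4.1.2 as the named secondary endpoint. State whether *response* in the objectives and in protocol 8.1.2 and 8.2.1 means confirmed response.
- In SAP 6.3.2, prespecify a parallel count and time-to-first analysis, by arm, of every restart of daily PE for a renewed platelet fall from 1 to 30 days after the last daily PE, regardless of confirmation. Show case 5 (recovered, unconfirmed) and case 6 (never reached 150,000/µL) separately.
- Include these events in the combined exacerbation and/or relapse count, and report complete remission with and without them as failures.
- Record the addition in SAP 6.1.5.
- Reconcile the study-drug and scheduling passages that use the term (protocol 7.2 and 8.1.2) with the stated definition. This review takes no position on how study drug should be handled.

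The cost is SAP text and a few extra outputs. Each PE session is already recorded (protocol 8.2.1.1) and platelets are measured daily during daily PE, so no new data are needed. The downside is that some added events may be the same episode continuing, and they depend on unblinded PE decisions. The two counts should therefore stand side by side, with neither replacing the other.

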## 1.2 Study Design

This is a Phase II multicentre, single-blinded, parallel design, randomised, placebo-controlled study. After confirmation of eligibility to study participation, adult subjects will be randomised in a ratio of 1:1 to either receive ALX-0081 or placebo as adjunctive therapy to PE. Adolescent subjects will not be randomised and will be treated with ALX-0081.

Adult subjects will receive a first intravenous (i.v.) bolus of 10 mg ALX-0081 or placebo via push injection within 6h, but not later than 15 minutes prior to the initiation of PE on study (which can either be the very first PE session, if the subject was randomised prior to the initiation of PE, or the second PE session, if the subject was randomised after one, single PE session). This first PE on study is followed by subcutaneous (s.c.) administration of 10 mg study drug. Adolescent subjects will receive weight-based doses according to the same administration schedule as adults.

Subsequently daily s.c. administrations of 10 mg ALX-0081 or placebo will follow each PE session for the duration of PE (including tapering and PE given for exacerbations) and once daily for 30 days following the last PE. The maximum total daily dose of study drug is 10 mg when administered in conjunction with PE (20 mg only in case twice daily PE sessions are needed) and 10 mg when in period following last PE. Study drug administration will continue in case of re-initiation of PE for an exacerbation of TTP with a maximum total treatment duration limited to 90 days after first administration of study drug. At 30 days after the last day of study drug administration, subjects will be assessed for the primary and secondary endpoints of the study and will be followed for a maximum of 1 year for relapses and other tertiary (longer-term) endpoints.

Laboratory parameters for inclusion, study conduct, safety assessments and assessments of response/relapse, re-treatment and study medication dose modification will be assessed at each local site laboratory.

[figure not shown]

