### 6.1.5 Changes to Planned Analyses from the Protocol

- Section 4.1.2 of the protocol describes the following secondary endpoint:  
Resolution or improvement (improvement of  $\geq 1$  grade in the CTCAE v4.0 scale) of TTP-related signs and symptoms as captured on the physical examination and as adverse events.  
  
At the time of writing this Statistical Analysis Plan, it is apparent from the design of the CRF that the CTCAE grade is recorded only once per event. Therefore it is not possible to determine if or when the CTCAE grade of a particular event has improved by  $\geq 1$  grade. As a consequence, for the adverse events part of this endpoint only resolution of events (defined as having a stop date and an outcome of either 'resolved' or 'resolved with sequelae') will be considered.
- Section 4.1.2 of the protocol describes the following secondary endpoint:  
Resolution of non-focal neurological symptoms as defined by neurocognitive function at complete remission, measured by a neurocognitive test battery.  
  
The intention was to define neurocognitive function as having a CNTB average summary score immediately post hospital discharge that is equal to or higher than at Baseline. At the time of writing this Statistical Analysis Plan, it is apparent from the data for the CNTB that the majority of subjects do not have their first CNTB assessment until after they have received study treatment. The time from first treatment to first CNTB assessment is not consistent across subjects, such that a homogeneous Baseline time point cannot be defined. It is therefore not appropriate to derive this endpoint based on change from Baseline because the resulting data will have no meaningful interpretation. It has been agreed that the CNTB will be summarised by descriptive statistics at each time point for actual results only; change from Baseline will not be calculated.

- Section 4.1.3 of the protocol describes the following secondary endpoint:  
Resolution of non-focal neurological symptoms as defined by neurocognitive function at one year follow-up, measured by a neurocognitive test battery.  

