The number and percentage of (subjects with) exacerbations of TTP at one month post first administration of study treatment, along with the exact binomial CI of the percentage will be presented by treatment group, overall and by ADAMTS13 activity  $< 5\%$  vs.  $\geq 5\%$  both at baseline and after last PE (measured on day 1 after last daily PE). The time to first exacerbation of TTP, from first study drug administration, will follow the same analysis method as the primary efficacy endpoint and will be presented graphically.

The number and percentage of subjects relapsing of TTP at one month post first administration of study treatment, along with the exact binomial CI of the percentage will be presented by treatment group, overall and by ADAMTS13 activity  $< 5\%$  vs.  $\geq 5\%$  both at baseline and after last PE (measured on day 1 after last daily PE). The time to first relapse of TTP, from first study drug administration, will be presented graphically.

The number and percentage of subjects with exacerbation and/or relapse, along with the exact binomial CI of the percentage will be presented by treatment group, overall and by ADAMTS13 activity  $< 5\%$  vs.  $\geq 5\%$  both at baseline and after last PE (measured on day 1 after last daily PE). The time to first exacerbation or relapse (whichever occurs first), for first study drug administration, will be presented graphically.

The number of daily PE sessions (all PE sessions during the daily PE period, which may include more than one PE per day), total volume of plasma administered, number of days

---

of PE (number of days with at least one PE administration) and number of consecutive days of PE (maximum number of days per subject where there was no interruption of PE) will be summarised descriptively by treatment group, overall, by ADAMTS13 activity < 5% vs.  $\geq$  5% at baseline and by having received first PE before randomisation or not.

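### SAP 6.3.2 counts complete remission, exacerbation and relapse one month after first dose instead of 30 days after end of study drug, so the relapse table is essentially empty by construction and later exacerbations are missed

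*SAP*

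**What the plan says.** Three places agree on the window. The heading over the secondary endpoints in SAP 6.3.2 reads "All endpoints achieved within 30 day period after end of study drug treatment", and protocol 4.1.2 has the same heading. SAP 1.2 says: "At 30 days after the last day of study drug administration, subjects will be assessed for the primary and secondary endpoints of the study".

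The analysis paragraphs under that SAP heading use a different anchor. They report "The number and percentage of subjects with complete remission at one month post first administration of study treatment", then the number and percentage of subjects with "exacerbations of TTP at one month post first administration of study treatment", then "The number and percentage of subjects relapsing of TTP at one month post first administration of study treatment".

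SAP 6.1.5, headed "Changes to Planned Analyses from the Protocol", lists three changes: the CTCAE-grade endpoint and two neurocognitive endpoints. The time point is not among them.

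Two further statements fix the timing. SAP section 3 describes relapse as: "Defined as de novo event of TTP that occurs later than 30 days after the last daily PE". SAP 1.2 places the first dose "within 6h, but not later than 15 minutes prior to the initiation of PE on study". Time to first exacerbation, measured from first dose, is to use the primary endpoint's analysis method. The primary analysis in SAP 6.3.1 censors at 30 days after first dose.

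**The concern.** The heading and the paragraphs cannot both be programmed. If the paragraphs are followed, relapse is counted over a period that ends before a subject can meet its definition. Exacerbation is counted over a period that ends before the risk period closes. Because complete remission requires the absence of exacerbation, each missed exacerbation can turn a subject into a complete remitter.

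Reducing exacerbations and relapses is a stated secondary objective. A relapse table of zeros in both arms could be read as a finding when it only reflects the window. Follow-up length also varies with how soon daily PE stops, and treatment is meant to change that, so the share of exacerbations lost can differ by arm.

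**Working it through.** **Plan's own figure.** The documents give no figure for these endpoints. The sample size in SAP 6.1.4 reproduces: with hazard ratio 6/3.36 = 1.786, one-sided 2.5% and 80% power, the Schoenfeld formula gives 4 × (1.960 + 0.842)² / (ln 1.786)² = 93.4 events. Then 93.4/0.85 = 109.9, that is 110. None of this depends on the secondary windows.

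**Relapse.** Let L be the days from first dose to last daily PE.
- The first dose precedes the first on-study PE, so L > 0.
- Relapse is possible only after day L + 30, which is later than day 30 for every subject with an on-study PE.
- At L = 3.36, 6 and 16 days, the earliest relapse is after day 33.4, 36 and 46.
- Relapse-eligible days by day 30 are therefore 0 in both arms.
- If one month is read as 31 days, simulation with the planning medians gives at most 0.10 eligible days per subject. At 33 days it gives under 0.8. Both maxima need daily PE to stop at the moment of response.
- Under the heading's window, with drug stopped on schedule and no tapering, observation runs to L + 30 + 30 = L + 60. That gives 30 eligible days per subject.

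**Exacerbation at fixed L.** The risk period runs from day L + 1 to day L + 30. The share seen by day 30 is (30 − (L + 1))/29:
- L = 3.36: 25.64/29 = 88%
- L = 6: 23/29 = 79%
- L = 8: 21/29 = 72%
- L = 16: 13/29 = 45%. Protocol 2.5.2 gives about 16 as the average number of treatments to remission; one per day is assumed here.

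No subject with an on-study PE has the whole period observed.

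**Exacerbations captured, by simulation.** Inputs from SAP 6.1.4: median times to response of 6 days (placebo) and 3.36 days (ALX-0081). Assumptions: exponential response times with response within 30 days; daily PE stopping 0, 2 or 4 days after response; exacerbation delay after last daily PE either uniform over days 1–30 or front-loaded (exponential, scale 10 days, truncated to days 1–30, mean about 9.3 days). Capture is the probability that L plus the delay is at most 30.

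| Daily PE stops | Uniform: placebo / ALX-0081 | Front-loaded: placebo / ALX-0081 |
|---|---|---|
| at response | 73.5% / 83.5% | 89.2% / 95.0% |
| 2 days later | 66.6% / 76.5% | 85.7% / 92.6% |
| 4 days later | 59.9% / 69.7% | 81.7% / 89.8% |

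**Effect on the comparison.** The ALX-0081/placebo risk ratio is multiplied by the ratio of the two captures.
- Same timing in both arms: from 95.0/89.2 = 1.07 to 69.7/59.9 = 1.16, against ALX-0081.
- Front-loaded on placebo but uniform on ALX-0081, as if the drug delayed exacerbations: 83.5/89.2 = 0.94, 76.5/85.7 = 0.89 and 69.7/81.7 = 0.85, in favour of ALX-0081.

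**Effect on remission.** The over-count is the exacerbation rate × (1 − capture). At an assumed 20% rate in both arms:
- placebo: 20 × (1 − 0.892) = 2.2 to 20 × (1 − 0.599) = 8.0 percentage points
- ALX-0081: 20 × (1 − 0.950) = 1.0 to 20 × (1 − 0.697) = 6.1 percentage points

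**The case against.** The best defence is that this is a drafting slip which the surrounding text would correct. The heading is right, the 1-month visit in SAP 1.3 is counted from the end of study drug, later paragraphs of 6.3.2 use that visit, and SAP 6.6 locks the first formal analysis on it. A programmer might follow the heading. That is plausible, but the table-level text names first administration three times, and it is the text that specifies each output. It needs correcting on either account.

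Three stronger readings are tempting, and the documents do not support them:
- *The error biases the results against ALX-0081.* This holds if exacerbation timing after the last daily PE is the same in both arms. Study drug continues for 30 days after the last PE and could delay exacerbations, and the direction can then reverse. The remission comparison above also assumes equal exacerbation rates.
- *Time to first exacerbation is cut at day 30.* The SAP says only that the method is the same as for the primary endpoint. Read literally, that includes the 30-day censoring, which would conflict with the heading. It can equally mean the stratified Kaplan-Meier and log-rank approach alone. The defect is that no censoring time is stated.
- *Relapse information is lost.* The time-to-relapse plot and the combined exacerbation and/or relapse count in 6.3.2 carry no day-30 limit. SAP section 4 lists relapse for up to 1 year. The longer-term sections are redacted, so further relapse tables cannot be excluded.

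It is also fair that the capture figures rest on assumed timing, and that SAP 6.3.2 calls these p-values purely exploratory.

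**Conclusion.** The SAP is wrong as written. The relapse result follows from its own definitions and needs no assumed rates: the count is essentially 0 versus 0. The exceptions are trivial: a month read as longer than 30 days, or a subject with no on-study PE.

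For exacerbation, loss of later events is certain in kind but uncertain in size. The ranges of roughly 60–89% (placebo) and 70–95% (ALX-0081) depend on the planning medians, daily PE stopping 0–4 days after response, and the assumed timing. Capture is lower if daily PE lasts longer. The loss can differ by arm, and its direction cannot be settled from the documents. For time to first exacerbation, the point is an unstated censoring horizon.

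The consequence is limited to exploratory secondary tables, but it should be corrected before database lock.

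**What to change.** In SAP 6.3.2, in the paragraphs on complete remission, exacerbation and relapse, replace the time point of one month after first administration with: *from first administration up to 30 days after last study drug administration (1-month follow-up)*. For time to first exacerbation, state that the primary endpoint's 30-day limit does not apply, and that subjects without an event are censored at the 1-month follow-up or last contact. If the earlier time point was intended, it must instead be declared and justified in SAP 6.1.5, and the relapse table at that time point dropped as uninformative.

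The cost is SAP wording and table programming. No extra waiting is needed: the first formal analysis (SAP 6.6) and the main study report (protocol 12.10) already wait for the 1-month follow-up. One limitation remains. Subjects who stop study drug early have a shorter observed period under the restored window, and a table footnote can say so.
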